The study will examine clinically anxious children's amygdala-mPFC response to fear faces when (A) the child's parent is beside them holding their hand during the fMRI scan (Parent-Present), and (B) the child is alone during the scan (Parent-Absent) (within-subjects design). Children with primary anxiety disorder diagnoses will serve as participants. Children will complete Parent-Present and Parent-Absent scans PRE- and POST-SPACE, or PRE- and POST-CBT (Cognitive-behavioral therapy), an established treatment of equal duration and therapist-parent contact.

Aim 1: Demonstrate SPACE lessens children's reliance on parents to reduce amygdala reactivity (i.e., target engagement).

Aim 2: Demonstrate associations between target engagement and anxiety outcomes.

Aim 3: Establish feasibility and acceptability of SPACE, as well as patient satisfaction.

2. Probable Duration of Project: 5 years.

3. Background: Describe the background information that led to the plan for this project.

Provide references to support the expectation of obtaining useful scientific data.

Anxiety disorders comprise the most prevalent disorders of childhood and adolescence. If not treated successfully, anxiety disorders cause significant short and long-term impairment and pose huge financial and societal costs (Costello, Egger, & Angold, 2005) through factors such as increased school dropout, teenage childbearing, and lost productivity in the workplace (Compton et al., 2004; Greenberg et al., 1999). Despite strong evidence for the efficacy of cognitive-behavior therapy (CBT), up to 50% of children remain symptomatic after treatment

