The study is a clinical trial involving children with primary anxiety disorders. Children will randomly be assigned to one of two treatment conditions.. One condition is Supportive Parenting for Anxious Childhood Emotions (SPACE) which focuses on reducing family accommodation of child anxiety symptoms. The comparator condition is cognitive-behavioral therapy (CBT) an established and evidence-based treatment for childhood anxiety disorders, of known efficacy. In CBT children will be introduced to and discuss the presenting problem, review treatment rationale and goals, work with the therapist to devise an anxiety hierarchy, and participate in in-session and out-of-session exposure tasks. Additionally, children will be introduced to the cognitive component of treatment by identifying faulty cognitions and generating incompatible self-statements, and exploring alternatives. . Families will be randomly assigned to one of the aforementioned conditions. After initial screening, children will first participate in a pre-treatment assessment (PRE). The PRE assessment will include: a structured interview with child and parent covering anxiety symptoms and related conditions, questionnaires completed by child and parent, a brief parent-child interaction which is video-taped, collection of blood and saliva (see procedures below). Following the PRE assessment, eligible patients will be randomized into either SPACE or CBT and will undergo a neuroimaging scan using fMRI to examine behavioral and brain processes associated with anxiety and fear processing.

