All parents who are interested in participating in this study will be administered a standardized telephone screen to ensure their child is experiencing anxiety problems and is eligible for MRI (including current psychiatric medications). The brief telephone screen will be completed by trained research assistants. If their child is experiencing anxiety problems and is eligible for MRI, the family will be scheduled for the Pre Assessment. After signing informed consent/assent forms, parents and youth will complete the ADIS: C/P. The purpose of the interview is to determine DSM-5 anxiety diagnoses and to rule out exclusionary diagnoses. The ADIS: C/P will be completed by one of the study's personnel. Cognitive testing administered by trained research personnel during the evaluation visit will be used to determine eligibility based on IQ. Eligibility will be determined after reviewing results of the ADIS: C/P and Pre Assessment with key study personnel at a staff meeting.

At the MRI visit, participants will again be given a thorough metal screening (Yale-MRRC MRI Safety Questionnaire) by trained research personnel to ensure that they are still eligible for the MRI (e.g., to rule out participants with a change in status of metal in the body, such as a child who recently got braces). At any time (during the phone screening prior to enrollment, or after enrollment in the study), the research personnel and the PI may determine that a participant is not fit to enroll in or continue in the study should they judge that it is in the participant's best interest to do so, if the participant begins a new medication or treatment that would change their eligibility, if they (or their parent) do not comply with the study plan, if they repeatedly miss appointments, if there is concern about their (or their parent's) ability to complete the interview and/or questionnaires validly and reliably, or for various other administrative reasons.

10. Risks: Describe the reasonably foreseeable risks, including risks to subject privacy, discomforts, or inconveniences associated with subjects participating in the research.

Interviews and questionnaires: Feeling upset when talking about anxiety or attending to anxious thoughts.

Behavioral Interactions: Temporary discomfort when discussing an issue on which child and mother disagree.

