- d. For multi-site studies for which the Yale PI serves as the lead investigator: N/A
 - i. How will adverse events and unanticipated problems involving risks to subjects or others be reported, reviewed and managed? Write here
 - ii. What provisions are in place for management of interim results? Write here
 - iii. What will the multi-site process be for protocol modifications? Write here

13. Statistical Considerations: Describe the statistical analyses that support the study design. General Overview. Data management protocols will be used to ensure data integrity. Missing values (including fMRI data) will be estimated using chained equation multiple imputation algorithms.¹⁰⁸ Analyses will focus on least squares test (OLS) of means and modern robust estimation procedures⁹⁴ that rely on Wilcox's R routines (which generally have more statistical power than traditional OLS)⁹⁵. If non-normality or outliers appear problematic, we will use the Wilcox functions base on M estimation. We will examine associations between arm and baseline variables to ensure successful randomization. Our analytic approach follows NIH guidelines on rigor and reproducibility, including analysis of sex as a potential covariate. Aim 1: Demonstrate target engagement. Child reliance on parent for amygdala reactivity reduction (calculated as the difference between amygdala reactivity to fear faces in the parent-absent compared to parent-present scan, and from hereon referred to as 'child reliance on parent') will decrease significantly from PRE to POST treatment for children whose parents participate in SPACE, as compared with children whose parents participate in CBT. The assessments of interest for this question are PRE and POST. The additional time-point (MID) will be useful to gain preliminary insights relating to more complex questions of mediation. The OLS analysis is a

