2-group single degree of freedom contrast between SPACE and CBT using child reliance on parent at PRE as a covariate to increase statistical power. The single degree of freedom contrast focuses on the comparison of covariate-adjusted means at POST. Of interest is whether the contrast between arms is statistically significant for child reliance on parent; the direction of change will be determined by the sign of the parameter estimates. A dummy variable for the two arms (SPACE, CBT) will be included in the OLS analysis, with randomization to SPACE scored 1 and randomization to CBT scored 0. A statistically significant negative parameter estimate of the effect of treatment arm on child reliance on parent indicates that reduction in child reliance on parent at POST is significantly greater following SPACE compared with CBT. The same analysis will be conducted for mPFC activation and for amygdala-mPFC functional connectivity.

SECTION II: RESEARCH INVOLVING DRUGS, BIOLOGICS, RADIOTRACERS, PLACEBOS AND DEVICES

If this section (or one of its parts, A or B) is not applicable, check off N/A and delete the rest of the section.

A. RADIOTRACERS ☒ N/A

B. DRUGS/BIOLOGICS ☒ N/A

B. DEVICES ☒ N/A

SECTION III: RECRUITMENT/CONSENT AND ASSENT PROCEDURES

1. Targeted Enrollment: Give the number of subjects:

- a. Targeted for enrollment at Yale for this protocol: 226 children and their mothers, for a total of 452 participants
- b. If this is a multi-site study, give the total number of subjects targeted across all sites:

Write here:

2. Indicate recruitment methods below. Attach copies of any recruitment materials that will be used.

- ☒ Flyers ☒ Internet/web postings ☐ Radio ☐ Tabling
☐ Posters ☐ Mass email solicitation ☐ Telephone
☒ Letter (postcard) ☒ Departmental/Center website ☐ Television
☐ X Blog posting with approved messaging/advertising
☐ Newsletter via email
☐ X messaging/advertising on music-listening platforms
☐ Medical record review* ☒ Departmental/Center research boards ☐ Newspaper
☒ Departmental/Center newsletters ☒ Web-based clinical trial registries ☒
 Clinicaltrials.gov
☒ YCCI Recruitment database
☒ Other: The Yale Child Study Center Anxiety & Mood Disorders Program sees children with anxiety disorders and those who meet study criteria will be offered the opportunity to

participate in the study. ☒ Social Media (Twitter/Facebook):

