*** Requests for medical records should be made through JDAT as described at**

<http://medicine.yale.edu/ycci/oncore/availableservices/datarequests/datarequests.aspx>

3. Recruitment Procedures:

- a. Describe how potential subjects will be identified. Children will be recruited through ongoing evaluations regularly conducted at the Yale Child Study Center. The YCSC has existed for over a century and is a major referral source for the community, treating children from all over Connecticut (as well as neighboring states). We therefore anticipate no difficulty in attaining the projected children and parents for this project. After a pre- treatment assessment (PRE), patients will be randomized into either parent-only treatment (SPACE) or child-only treatment (CBT).
- b. Describe how potential subjects are contacted. Parents who are interested in enrolling their child in the study will make initial contact. A phone screen will be administered by a study personnel member to ensure their child is experiencing anxiety difficulties and is eligible for MRI.
- c. Who is recruiting potential subjects? The study personnel including PI and research assistants will be responsible for recruiting potential subjects.

4. Assessment of Current Health Provider Relationship for HIPAA Consideration:

Does the Investigator or any member of the research team have a direct existing clinical relationship with any potential subject?

- ☐ Yes, all subjects
☒ Yes, some of the subjects
☐ No

If yes, describe the nature of this relationship. Some participants may have been assessed or treated by members of the research team in the past.

5. Request for waiver of HIPAA authorization: (When requesting a waiver of HIPAA Authorization for either the entire study, or for recruitment purposes only. Note: if you are collecting PHI as part of a phone or email screen, you must request a HIPAA waiver for recruitment purposes.)

Choose one:

- ☐ For entire study
☒ For recruitment/screening purposes only
☐ For inclusion of non-English speaking subject if short form is being used and there is no translated HIPAA research authorization form available on the University's HIPAA website at hipaa.yale.edu.

- i. Describe why it would be impracticable to obtain the subject's authorization for use/disclosure of this data: It would be impractical to obtain the subject's

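### The first fMRI scan, which supplies the Aim 1 baseline covariate, appears to follow randomisation, and nothing keeps allocation concealed until it is done

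*Combined protocol and SAP*

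**What the plan says.** Section I, item 4 (Research Plan) gives the content of the first assessment: "The PRE assessment will include: a structured interview with child and parent covering anxiety symptoms and related conditions, questionnaires completed by child and parent", followed by a video-taped interaction and blood and saliva collection. No scan is listed. The next step is: "Following the PRE assessment, eligible patients will be randomized into either SPACE or CBT and will undergo a neuroimaging scan using fMRI".

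Section III, item 3a (Recruitment Procedures) also places randomisation after the PRE assessment: "patients will be randomized into either parent-only treatment (SPACE) or child-only treatment (CBT"). It does not mention the scan.

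Section I, item 1 (Statement of Purpose) labels the scans by treatment: "Children will complete Parent-Present and Parent-Absent scans PRE- and POST-SPACE, or PRE- and POST-CBT".

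Section I, item 13 (Statistical Considerations) defines child reliance on parent from the scans: "calculated as the difference between amygdala reactivity to fear faces in the parent-absent compared to parent-present scan". The Aim 1 model is described as follows: "2-group single degree of freedom contrast between SPACE and CBT using child reliance on parent at PRE as a covariate to increase statistical power". It is also to be run for mPFC activation and for amygdala-mPFC connectivity. Item 13 also plans to compare the arms on baseline variables as a check on randomisation, and to impute missing values, fMRI data included.

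On fitness to be scanned, Section I, item 9 says: "At the MRI visit, participants will again be given a thorough metal screening". Under item 4, children who do not complete the scan may do the tasks outside the scanner.

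**The concern.** Covariate adjustment in a randomised comparison relies on the covariate being untouched by allocation. A baseline measured before randomisation has this property by design. One measured afterwards has it only if knowledge of the arm cannot affect it.

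That is open to doubt here. The score contrasts the child's amygdala response alone with the response while a parent sits beside them holding their hand. One arm is a treatment given to the parent, aimed at reducing accommodation of the child's anxiety. A family that has just been told it is in that arm might behave differently during the parent-present run. The main Aim 1 contrast would then be adjusted for something allocation had already moved.

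The order also affects who is randomised. A child found unfit for MRI on the scan day, or unable to finish the scan, would already have an arm but no measured PRE value.

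**Working it through.** **Order of events.** No section puts the scan before randomisation. Four features of the protocol suggest that it is not part of the PRE assessment:
- Item 4 lists the PRE content without it.
- Item 4 (Assessment Procedures) has PRE, MID and POST each done in a single clinic session, whereas the scan is at an imaging centre and is scheduled only after simulator training.
- Item 4 describes the second scan as an addition to the POST assessment.
- Section V (Payments) pays for the first MRI visit as a visit of its own.

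No section says when families or scan staff learn the allocation.

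**Bias formula.** The adjusted contrast is

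adjusted difference = (POST difference between arms) − b × (PRE difference between arms),

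where b is the within-arm slope of POST on PRE. With a PRE score taken before randomisation, the expected PRE difference is zero. If allocation shifts the PRE score by d, the contrast departs from the effect of assignment by −b × d.

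**Inputs.** The documents give neither b nor d, so both are assumed: b from 0.2 to 0.5 and d from 0.1 to 0.3 SD, with equal SDs at PRE and POST so that b equals the PRE-POST correlation r.
- Smallest: 0.2 × 0.1 = 0.02 SD.
- Largest: 0.5 × 0.3 = 0.15 SD.

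A PRE score raised in SPACE biases the contrast in favour of SPACE; a lowered score does the reverse.

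**Comparison figure.** The protocol gives no alpha, power, effect size or allocation ratio, so there is no stated calculation to reproduce. Assume two-sided 5%, 80% power, 1:1 allocation and all 226 targeted children analysed:

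detectable effect = (1.96 + 0.842) × √[(4/226) × (1 − r²)]
- r = 0.5: 2.802 × √(0.01770 × 0.75) = 0.323 SD.
- r = 0.2: 2.802 × √(0.01770 × 0.96) = 0.365 SD.
- No covariate: 2.802 × √0.01770 = 0.373 SD.

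With the same r on both sides, the largest bias is 0.15/0.323 = 46% of the detectable effect and the smallest is 0.02/0.365 = 5%.

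**Simulation** (4,000 runs, 113 per arm, no true POST effect, nominal 5% test):

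| r | shift in PRE (SD) | mean estimate (SD) | rejection rate |
|---|---|---|---|
| 0.5 | 0 | 0.000 | 0.053 |
| 0.3 | 0.2 | −0.059 | 0.074 |
| 0.5 | 0.2 | −0.099 | 0.140 |
| 0.5 | 0.3 | −0.148 | 0.246 |

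These agree with −b × d. With no shift, as when the scan comes first, the model is unbiased.

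**Baseline check.** An arm difference in PRE reliance could be chance, faulty randomisation or a reaction to allocation. For a score taken after allocation, the item 13 comparison cannot tell these apart.

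**Scan-day failures.** The documents give no failure rate. As an illustration only, if 10% or 30% of children were lost completely from 113 per arm and the rest analysed without a covariate, the detectable effect would rise from 0.373 to 0.393 or 0.445 SD.

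**The case against.** The strongest reply is that the order is not fixed by the text. The Research Plan joins randomisation and scan with an 'and', not a 'then'. Section I, items 1 and 13 treat the scan-derived score as a PRE measure, and Section III, item 3a randomises after PRE. If PRE includes the scan, the scan comes first. That ambiguity is real. A reader might infer that the protocol definitely scans after randomisation; the documents support only that it appears to, and that they allow it.

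A reader might also infer that the Aim 1 contrast is biased because its covariate is measured late. That does not follow. The arm must be known before the scan, and knowing it must change the score before any session has been delivered. The documents are silent on the first and give no evidence for the second.

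Two readings of the numbers also go too far. The 226 is targeted enrolment, and consent precedes the diagnostic interview and IQ testing, so fewer may be randomised. Nor can the bias be computed with a steeper slope than the correlation used for the detectable effect, since under equal SDs they are the same quantity.

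On losses, MRI contraindications are exclusion criteria screened by telephone, the mock scan removes claustrophobic children, and missing fMRI data are to be imputed. Loss unrelated to arm costs precision and does not bias the contrast. These safeguards reduce the problem but do not remove it: the metal screen is repeated at the MRI visit because status can change, and a mock scan cannot catch every failure in the real one.

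**Conclusion.** The point holds as a weakness in sequence and concealment, not as a demonstrated bias. As written, the plan allows the scan-based covariate in its main Aim 1 model, and in the parallel mPFC and connectivity models, to be measured after the family knows its arm. If that knowledge shifts the score, the contrast moves by 0.02 to 0.15 SD under the assumed slopes and shifts, against a detectable effect of about 0.32 to 0.37 SD. If the arm is unknown at the scan, or knowing it changes nothing, the bias is zero.

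The point about scan failures does not depend on that assumption. If the scan follows randomisation, any child who fails the scan-day screen or does not complete the scan is a randomised child whose PRE value must be imputed. How many there would be cannot be derived from the documents.

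**What to change.** Amend Section I, item 4 and Section III, item 3a so that the first scan visit is completed before randomisation. Failing that, state that allocation is not disclosed to families or scan staff until the scan is done. Concealment alone protects the covariate; only scanning first also brings scan-day failures to light before allocation. A change in metal status found then would fall under the existing MRI exclusion in Section I, item 8.

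Do not make a usable scan a new condition of entry. Item 4 provides for children who do not finish the scan, or whose parent cannot enter the scanner room, to do tasks outside it, and a usable-scan rule would exclude them.

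For children already randomised, record whether allocation was disclosed before the first scan. Add to Section I, item 13 a sensitivity analysis of the POST arm contrast without the PRE-scan covariate.

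The cost is an amendment to the order of existing steps, and families learn their treatment slightly later. The sensitivity analysis is less precise: under the same assumptions its detectable effect is 0.373 SD, against 0.323 (r = 0.5) to 0.365 (r = 0.2) with the covariate.

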In the SPACE treatment condition parents participate in 12 weekly parent-only sessions. In the CBT treatment condition children participate in 12 weekly child-only sessions. Parents of children assigned to CBT will meet with the child's therapist three times over the course of the treatment study, to be kept informed about their child's progress and provide helpful information to the therapist. Sessions can take place in person at the Yale Child Study Center or over secure video-link using the HIPAA approved Zoom software provided by Yale University. Participants will choose whether to have the sessions in person or over zoom and can elect to have some in person and some over Zoom. Youth and parents will be re-assessed after 6 treatment sessions (MID) and after the 12th session (POST). These assessments include the same procedures done at the first assessment, except the MID assessment does not include clinical interviews. After the 12th treatment session children will also undergo a second neuroimaging scan using fMRI. In both treatment conditions participants will be invited back for a follow-up visit 6-months from their initial appointment. At this appointment, these assessment procedures are the same as the MID assessment, but does not include a video-taped interaction or saliva sample.

Participants who are already enrolled will be invited to electronically complete an optional set of questionnaires related to their experiences during the COVID-19 pandemic (Please see Measures for list of questionnaires). This part of the study is completely optional. The questionnaires will be administered via the HIPAA-secure REDCap platform. Participants will receive \$15 when they submit the completed questionnaires.

Assessment Procedures:

Each of these three assessments (PRE, MID, POST) will be conducted in single sessions at our clinic by carefully trained independent evaluators (IE). Each assessment session will include collection of biological samples, behavioral observation, and self-report measures. During the youth interview, the parent will be administered the questionnaires and vice versa.

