Attention Bias to Threat. Attention bias to threat will be assessed with a probe-detection task using the computer software Eprime. Participants (both mother and child) will complete tasks using a provided laptop computer and mouse. A centered fixation cross will appear first and will be followed immediately by two faces of the same actor expressing different emotions, one above the other. Participants will be told that a probe (< or >) will appear on the screen and that their task is to push the corresponding mouse button

Blood Samples:

Subjects will be asked to provide us with a small blood sample for our research during the initial appointment, and again at the 6-month follow up appointment. The total amount drawn will be less than one ounce each time. An experienced and qualified professional will draw the blood from a vein near the elbow.

We will also ask for permission to store blood samples for future research projects. If the subject agrees, the blood will be stored in a safe place without personal identification and retained for future research purposes.

Saliva Sample

To collect a sample of saliva we will subjects to chew on a small cotton swab for about one minute, then spit it out into a special sterile container.

MRI:

All participants will be scanned using a 3T scanner located at the Yale Magnetic Resonance Research Center or Yale's Brain Imaging Center. We train children on the tasks in a simulator so that they can acclimate to the scanning environment. Prerecorded scanner sounds will be played as the participant is in the simulator. We will describe and answer any questions the child or parent has about the MRI procedure. The simulator is a replica of the 3T scanner and includes speakers for simulating sounds, a screen to simulate visual stimuli, and a motorized table for simulating experiences the participant will have in the actual scanner. The participant

will watch videos and practice the computer tasks while in the simulator. Only after acclimating the child to the scanner environment so that both the child and parent are comfortable with the procedure, will the child be scheduled for the actual scan. Otherwise the study will be terminated.

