To minimize risk relating to questionnaire and interview assessments: It is possible that some children and adolescents and parents may become slightly anxious or upset when asked to attend to their anxious thoughts or feelings as required by these procedures. We anticipate such reactions will be short-lived in nature and typically have no significant long-term consequences. In fact, many children and parents are likely to benefit from an improved self-understanding derived from the completion of these measures. These measures are standard and widely used in this age range, and there have been no reports of negative iatrogenic effects. Participants and their parents are not required to answer questions during interviews or on questionnaires that they find too sensitive.

To minimize risk relating to blood draw: Venipuncture will be performed by qualified and experienced personnel in an approved location at the Yale University Department of Laboratory Medicine. Trained, qualified and experienced personnel reduce the risk of pain, bleeding, redness, inflammation, ecchymosis, phlebitis and infection. Qualified locations reduce risks that accompany fainting. The amount of blood to be drawn, not more than 15ml, is well within what is permissible and should not present risk. Participants will be able to decline to have the blood draw at any time until it is completed.

To minimize risk relating to behavioral interactions: Parent and child will each be able to terminate the entire interaction, or part of it at any time. Children and parents will be given instructions that they may stop whenever they want. The graduate research associates also have been carefully and thoroughly trained in the providing of reassurance. Similar procedures have been widely used for many years without report of negative results. In addition, the research associate will spend some time with the participants following each assessment procedure and discuss the participants' reactions to the procedure.

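### The protocol is inconsistent about which visits include a blood draw, and its risk statement cites a volume limit about half the per-draw limit given elsewhere, without saying whether it is per draw or in total

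*Combined protocol and SAP*

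**What the plan says.** **Schedule.** In Section I, item 4 (Research Plan), the PRE assessment includes "collection of blood and saliva (see procedures below". Of MID and POST the same item says: "These assessments include the same procedures done at the first assessment, except the MID assessment does not include clinical interviews". Of the 6-month visit it says: "At this appointment, these assessment procedures are the same as the MID assessment, but does not include a video-taped interaction or saliva sample". Under Assessment Procedures, with reference to PRE, MID and POST, it adds: "Each assessment session will include collection of biological samples, behavioral observation, and self-report measures". The later Blood Samples text gives its own schedule: a "small blood sample for our research during the initial appointment, and again at the 6-month follow up appointment".

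**Volume.** Blood Samples says: "The total amount drawn will be less than one ounce each time". Section I, item 11 (Minimizing Risks) says: "The amount of blood to be drawn, not more than 15ml, is well within what is permissible and should not present risk".

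**Status of the draw.** Section I, item 10 (Risks) makes the blood draw optional, and item 11 lets participants decline it until it is completed. The subjects include children aged 6 to 12 (item 6, Subject Population).

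**The concern.** The number of research venipunctures depends on which part of the Research Plan is followed. Blood Samples names two visits. The visit descriptions take out interviews, video and saliva by name where they are not wanted, and never take out blood. Staff working from the visit descriptions could draw at MID and POST; staff working from Blood Samples would not.

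The reassurance about risk is tied to 15 ml, while the procedure text allows nearly twice that at one draw, and no cumulative figure appears anywhere. A family deciding whether to accept an optional draw, and an IRB judging the risk statement, both need a consistent number of draws and a consistent volume.

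**Working it through.** **1. Count the draws.**

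| Visit | Visit descriptions, read literally | Blood Samples |
|---|---|---|
| PRE / initial | Blood listed | Blood listed |
| MID | PRE procedures less clinical interviews: blood stays in | Not listed |
| POST | PRE procedures: blood stays in | Not listed |
| 6 months | MID less video and saliva: blood stays in if MID has it | Blood listed |
| Draws | 4 (by inference) | 2 |

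**2. Test whether some reading of MID reconciles them.** Take Blood Samples as the full list of draws and the 6-month description as the full definition of that visit. There are two cases.

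- MID includes blood. Then Blood Samples leaves out at least the MID draw.
- MID does not include blood. The 6-month visit is obtained from MID by subtraction only, so it has no blood either. Blood Samples says it does.

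Neither case makes both texts true. This step does not depend on what is meant by biological samples.

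**3. Compare the volume limits.** Inputs: less than one ounce per draw (Blood Samples); at most 15 ml, basis not stated (Minimizing Risks); 1 US fluid ounce = 29.57 ml, a unit conversion that the protocol does not give.

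- 15 / 29.57 = 0.51 ounce. A draw of up to 15 ml therefore also meets the one-ounce limit.
- 29.57 / 15 = 1.97. The Blood Samples limit for one draw is about twice the volume on which the risk statement rests.

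**4. Cumulative ceiling on the two-draw schedule.**

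| Reading | Calculation | Ceiling |
|---|---|---|
| 15 ml is the study total | 15 (on average 15 / 2 = 7.5 per draw) | 15 ml |
| 15 ml is per draw | 2 × 15 | 30 ml |
| One-ounce limit per draw | 2 × 29.57 | less than 59.1 ml |

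The highest is 59.1 / 15 = 3.9 times the lowest.

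**5. Check for an effect on the analysis.** Neither the three aims (item 1, Statement of Purpose) nor Statistical Considerations (item 13) uses a blood measure. Item 5 (Genetic Testing) mentions plasma for oxytocin levels and oxytocin-receptor genotyping, but specifies no analysis of change.

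**The case against.** The best defence is that the specific text governs the general. The PRE description points ahead to the procedures, and Blood Samples there gives a definite two-visit schedule. No passage states four draws; that count is chained from wording about repeating procedures. Saliva alone would satisfy the reference to biological samples. The two volumes are both upper limits and can be met together. The draw is optional.

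Much of this stands. Four draws is an inference, the biological-samples sentence proves nothing about blood, and the schedule cannot fairly be called absent, because Blood Samples gives one. But preferring that text only chooses between the two descriptions. If blood is removed from MID, the visit description gives none at 6 months, so it still needs correcting. If Blood Samples is instead read as not exhaustive, it is incomplete as a schedule. Optional status does not settle how many draws a family is being asked to accept.

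Three stronger readings are tempting and are not supported:

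- A reader might infer that the two volumes contradict each other. They do so only if 15 ml is a total while up to an ounce is planned each time, and the text does not establish either.
- A reader might multiply the one-ounce limit by four draws, or scale the result to body weight. That joins a limit from one text to a schedule that text does not give, sets aside the 15 ml limit, and needs a weight the documents do not supply.
- A reader might infer that having no blood draw at POST undermines an oxytocin result. The plan contains no aim or analysis of oxytocin change to undermine.

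**Conclusion.** The blood-draw schedule is inconsistently defined: two draws in Blood Samples, four by inference from the visit descriptions. The conflict holds whichever way MID is read, provided Blood Samples is taken as the complete list and the 6-month description as a complete definition.

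The volume issue is narrower. There are two unequal ceilings, one with no stated basis, and the risk statement uses the smaller. On the two-draw schedule the cumulative ceiling is 15 ml, 30 ml or just under about 59 ml depending on the reading, assuming US fluid ounces.

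This should be corrected because it concerns research venipuncture in children and the accuracy of what is said about its risk. It does not touch the trial's planned analyses or conclusions. This review does not say which schedule or volume is right.

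**What to change.** Reconcile the PRE, MID, POST and 6-month descriptions, Blood Samples and Minimizing Risks. A short visit table would do it: for each of the four visits, state whether blood is drawn, and do not leave this to be inferred from wording about repeated procedures or biological samples. Give one volume limit, labelled as a maximum per draw and a cumulative maximum, and restate the risk statement against the cumulative figure. The choice of schedule and volume stays with the sponsor and the IRB.

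The consent and assent forms were not available for this review; they should be checked against the reconciled text. The cost is a wording amendment, with no extra visits or staff.
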